### 6.14.2. Extent of Exposure

Exposure, including total patient-years of exposure, will be calculated for Study JAIM. Duration of exposure to study drug will be summarized using descriptive statistics (n, mean, standard deviation [SD], minimum, first quartile, median, third quartile, maximum). Cumulative

exposure and duration of exposure will be summarized in terms of frequency counts and percentages by category and treatment group.

Total patient-years of exposure (PYE) will be reported for each treatment group for overall duration of exposure. Exposure will also be classified by the frequency of patients falling into different exposure ranges. Exposure ranges will generally be reported in weeks using the following as a general guide:

- $\geq 4$  weeks,  $\geq 16$  weeks,  $\geq 24$  weeks,  $\geq 52$  weeks,  $\geq 84$  weeks, and  $\geq 156$  weeks.
- $>0$  to  $<4$  weeks,  $\geq 4$  weeks to  $<16$  weeks,  $\geq 16$  weeks to  $<24$  weeks,  $\geq 24$  weeks to  $<52$  weeks,  $\geq 52$  weeks to  $<84$  weeks,  $\geq 84$  weeks to  $<156$  weeks, and  $\geq 156$  weeks.

Overall exposure in JAIME will be summarized in total PYE which is calculated according to the following formula:

$$\text{Total PYE} = \text{sum of duration of exposure in days (for all patients in treatment group)} / 365.25$$

Additionally, time spent in the study will be summarized with descriptive statistics (n, mean, SD, minimum, first quartile, median, third quartile and maximum).

### **6.14.3. Clinical Laboratory Evaluation**

For the categorical analysis, the analysis period is defined as the treatment period plus up to 30 days off-drug follow-up time. The analysis period for the continuous by-visit analyses (eg, change from baseline by visit) is defined as the treatment period excluding off-drug follow-up time. Refer to the iSAP for more details. The following analyses are planned:

- clinical laboratory evaluation in terms of box plots and treatment-emergent summaries.

### **6.14.4. Vital Signs and Other Physical Findings**

For the categorical analysis, the analysis period is defined as the treatment period plus up to 30 days off-drug follow-up time. The analysis period for the continuous by-visit analyses (eg, change from baseline by visit) is defined as the treatment period excluding off-drug follow-up time. Refer to the ISAP for more details. The following analyses are planned:

- vital signs in terms of box plots and treatment-emergent summaries.

### **6.14.5. Special Safety Topics, Including Adverse Events of Special Interest**

Special safety topics will be analyzed in the context of combining the safety data from the originating Studies JAHZ and JAIA with the safety data from Study JAIME. The planned analyses are described in the ISAP.

For the purposes of the CSR for Study JAIME alone, the summaries of infections and type of infections will be provided.

The following summaries for each treatment group will be included in the overview of infections:

- patients with  $\geq 1$  treatment-emergent (TE) infection
- serious infections
- AEs that led to
  - permanent discontinuation from study drug, and
  - temporary interruption from study drug
- TE opportunistic infection
- TE herpes zoster
- TE herpes simplex
- TE tuberculosis, and
- TE viral hepatitis.

### 6.15. COVID-19 Trial Impact

Patients who experience an impact to their trial participation due to quarantine and/or travel restrictions related to COVID-19 will have their type of impact summarized.

COVID-19-specific impacts for summarization include protocol deviations, including out of window visits, treatment interruptions, treatment and/or study discontinuations, and missed visits, regardless of whether or not the patient has a COVID-19 infection documented as an AE.

The proportion of patients impacted in each category will be summarized. This summary will be provided for the overall mITT patients as well as by region. The number of patients who missed visits related to COVID-19 will be summarized by visit.

The following by-patient listings will be provided

- listing of study and treatment disposition related to COVID-19
- listing of important/nonimportant protocol deviations due to COVID-19
- listing of COVID-19 AEs (based on Standardized Medical Dictionary for Regulatory Activities Query [SMQ] 20000237 using the narrow-term classification)
- listing of temporary treatment interruptions related to COVID-19, and
- listing of missed visits related to COVID-19.

### 6.16. Protocol Violations

Protocol deviations will be identified throughout the study. Important protocol deviations (IPDs) are defined as those deviations from the protocol that would potentially compromise patient safety, data integrity, or study outcome.

A by-patient listing of IPDs will be provided.

A summary of the number and percentage of patients with an important protocol deviation by treatment group, overall, and by type of deviation will be provided.

### 6.17. Data Monitoring Committee

A data monitoring committee (DMC) will oversee the conduct of all the Phase 3 clinical trials evaluating baricitinib in patients with SLE. The DMC will consist of members external to Lilly.

This DMC will follow the rules defined in the DMC charter, focusing on assessing safety data for baricitinib. The same DMC will monitor safety-related data for ongoing studies of baricitinib in other indications.

Details of unblinding are given in Section 7 and the DMC charter.

### **6.18. Annual Report Analyses**

Based on regulatory requirements for the Development Safety Update Report (DSUR), reports will be produced (if not already available from the CSR) for the reporting period covered by the DSUR.

### **6.19. Clinical Trial Registry Analyses**

Additional analyses will be performed for the purpose of fulfilling the Clinical Trial Registry (CTR) requirements.

Analyses provided for the CTR requirements include the following:

- Summary of AEs, provided as a dataset which will be converted to an XML file. Both SAEs and ‘Other’ AEs are summarized by treatment group and by MedDRA PT.
- An AE is considered ‘Serious’ whether or not it is a TEAE.
- An AE is considered in the ‘Other’ category if it is both a TEAE and is not serious. For each SAE and ‘Other’ AE, for each term and treatment group, the following are provided:
  - the number of participants at risk of an event
  - the number of participants who reported each event term
  - the number of events experienced.

Consistent with [www.ClinicalTrials.gov](http://www.ClinicalTrials.gov) requirements, ‘Other’ AEs that occur in fewer than 5% of patients/subjects in every treatment group may not be included if a 5% threshold is chosen (5% is the minimum threshold).

## 7. Unblinding Plan

Unblinding details are specified in a separated blinding/unblinding plan.

## 9. Appendices

---

## Appendix 1. Selection of Medications

---

The following categories of medication are required. For each category, instructions for selecting the correct medications are given.

### Corticosteroids

The following ATC codes will be used to select all possible systemic corticosteroids:

- H02 Corticosteroids for systemic use (except H02AA Mineralocorticoids), specifically
  - H02AB Glucocorticoids
  - H02BX Corticosteroids for systemic use, combinations
  - H02CA Anticorticosteroids,

and additionally

- M01BA Anti-inflammatory/antirheumatic agents in combination with corticosteroids

All unique preferred names in the database falling under the above ATC codes will be reviewed by the Lilly Medical Group in order to determine which ones should be included.

For each patient who has recurrent, intravenous injection of any corticosteroids with a start date or stop date during the treatment period (ie, from the date of randomization to the day of completion/early termination), the medications for this patient will be reviewed and the patient will be classified as having “prohibited” or “not prohibited” use during the treatment period.

Note: determination of prohibited use is based on a case-by-case assessment of recurrent intravenous corticosteroid use, considering if dose and/or duration of use are clinically relevant.

All corticosteroid doses need to be converted to prednisone equivalent doses. If additional conversion factors are required, these will be added to the table below in a SAP revision prior to database lock.

The following table should be used for converting nonprednisone medications to prednisone equivalent:

Multiply the dose of the corticosteroid taken by the patient (in milligrams) in Column 1 by the conversion factor in Column 2 to get the equivalent dose of prednisone (in milligrams).

*Example: Patient is taking 16 mg of methylprednisolone po daily. To convert to prednisone:  $16 \text{ mg methylprednisolone} \times 1.25 = 20 \text{ mg prednisone}$ . 16 mg of methylprednisolone po daily is equivalent to 20 mg of prednisone po daily.*

Column 1	Column 2
Corticosteroid Preferred Name	Conversion factor for converting to an equivalent prednisone dose
Prednisone	1
Prednisone acetate	1
Prednisolone	1
Prednisolone acetate	1
Prednisolone sodium phosphate	1
Methylprednisolone	1.25
Methylprednisolone acetate	1.25
Methylprednisolone sodium succinate	1.25
Triamcinolone	1.25
Triamcinolone acetonide	1.25
Triamcinolone hexacetonide	1.25
Cortisone	0.2
Cortisone acetate	0.2
Hydrocortisone	0.25
Hydrocortisone acetate	0.25
Hydrocortisone sodium succinate	0.25
Betamethasone	6.25
Betamethasone acetate	6.25
Betamethasone dipropionate	6.25
Betamethasone sodium phosphate	6.25
Dexamethasone	6.25
Dexamethasone acetate	6.25
Dexamethasone phosphate	6.25
Dexamethasone sodium phosphate	6.25
Paramethasone	2.5
Deflazacort	0.83
Celestona bifas	6.25
Depo-medrol med lidokain	1.25
Diprosan	6.25
Fluocortolone	1
Meprednisone	1.25

**Antimalarials**

The following ATC codes will be used to select all possible antimalarials:

- P01B Antimalarials, specifically
  - P01BA Aminoquinolines
  - P01BB Biguanides
  - P01BC Methanolquinolines
  - P01BD Diaminopyrimidines
  - P01BE Artemisinin and derivatives, plain
  - P01BF Artemisinin and derivatives, combinations
  - P01BX Other antimalarials
- M09AA Quinine and derivatives

All unique preferred names in the database falling under the above ATC code will be reviewed by the Lilly Medical Group in order to determine which ones should be included.

For patients who have at least 1 new antimalarial with a start date or stop date during the treatment period (ie, from the date of randomization to the day of completion/early termination), all antimalarial medications for this patient will be reviewed and the patient will be classified as having “prohibited” or “not prohibited” use during the treatment period. Note: determination of prohibited use is based on a case-by-case assessment of new antimalarial use, considering if dose and/or duration of use are clinically relevant (eg, switch from hydroxychloroquine to equivalent dose of chloroquine is not prohibited).

**Immunosuppressants**

The following ATC codes will be used to select all possible immunosuppressants:

- M01AX Other antiinflammatory and antirheumatic agents, non-steroids. Note: for M01AX, only if the medication preferred name is sulfasalazine
- M01C Specific Antirheumatic Agents, specifically
  - M01CA Quinolines
  - M01CB Gold preparations
  - M01CC Penicillamine and similar agents
  - M01CX Other specific antirheumatic agents
- L01AA Nitrogen mustard analogues
- L01BA Folic acid analogues
- L04AA: Selective immunosuppressants
- L04AD Calcineurin inhibitors

- L04AX Other immunosuppressants
- J04BA Drugs for Treatment of Lepra

All unique preferred names in the database falling under the above ATC codes will be reviewed by the Lilly Medical Group in order to determine which ones should be included.

For patients who have at least 1 new immunosuppressant medication with a start date or stop date during the treatment period (ie, from the date of randomization to the day of completion/early termination), all immunosuppressant medications for this patient will be reviewed and the patient will be classified as having “prohibited” or “not prohibited” during the treatment period. Note: determination of prohibited use is based on a case-by-case assessment of new immunosuppressant use, considering if dose and/or duration of use are clinically relevant (eg, switch from methotrexate oral daily dose to equivalent weekly injection is not prohibited).

### **Intravenous immunoglobulin**

The following ATC code will be used to select all immunoglobulins:

- J06B Immunoglobulins (excluding J06BB as unlikely to be IV)

### **Biologics**

The following ATC code will be used to select all biologics:

- L01XC Monoclonal antibodies
- L01XX Other antineoplastic agents
- L04AA Selective immunosuppressants
- L04AB Tumor necrosis factor alpha (tnf-) inhibitors
- L04AC Interleukin inhibitors
- M01CX Other specific antirheumatic agents
- M05BX Other drugs affecting bone structure and mineralization
- V98 Investigational drug

All unique preferred terms in the database falling under the above ATC code will be reviewed by the Lilly Medical Group in order to determine which ones should be included.

### **NSAIDs**

The following ATC codes will be used to select all NSAIDs:

- M01 Anti-inflammatory and Antirheumatic Products, specifically
  - M01AA Butylpyrazolidines
  - M01AB Acetic acid derivatives and related substances
  - M01AC Oxicams

- M01AE Propionic acid derivatives
- M01AG Fenamates
- M01AH Coxibs
- M01BX Other antiinflammatory/antirheumatic agents in combination with other drugs
- M09AX Other drugs for disorders of the musculo-skeletal system

**Live Vaccines**

All medications falling under the following ATC code should be selected and reviewed by the Lilly medical group so that they can confirm which are live vaccines:

- J07 Vaccines

## Appendix 2. Baseline Measures and Patient Characteristics

This appendix itemizes the specific baseline measures and patient characteristics to be presented and how they will be summarized. Changes to [Table JAIM.APP.1](#), including the summary of additional patient characteristics, will not require an amendment to the SAP.

**Table JAIM.APP.1 Summary Tables Related to Patient Characteristics**

Variable	Continuous Summary	Categorical Summary a	Included in Interim 1 Analysis/Derivation
Age b	Yes	<65 years, ≥65 to <75 years, ≥75 to <85, ≥85; ≥65; ≥75; <40 years, ≥40 years;	Yes
Sex	No	Male, Female	Yes
Ethnicity (US only)	No	Hispanic/Latino, Non-Hispanic/Non-Latino	Yes
Race	No	American Indian/Alaska Native, Asian, Black/African American, Native Hawaiian or other Pacific Islander, White, or Multiple	Yes
Geographic Region	No	North America, Central/South America/Mexico, Europe, Asia, Rest of World	Yes
Country	No	By country	Yes
Height (cm)	Yes	None	Yes
Waist circumference (cm)	Yes	None	Yes
Weight (kg)	Yes	<80 kg, ≥80 kg	Yes
		<100 kg, ≥100 kg	Yes
BMI at Visit 2 c	Yes	Underweight (<18.5 kg/m  ), Normal (≥18.5 and <25 kg/m  ), Overweight (≥25 and <30 kg/m  ), Obese (≥30 and <40 kg/m  ), Severely obese (≥40 kg/m  )	Yes

## Summary Tables Related to Patient Characteristics

Variable	Continuous Summary	Categorical Summary a	Included in Interim 1 Analysis/ Derivation
Baseline Disease Characteristics			
Time since diagnosis of lupus (years) e	Yes	<1 year, ≥1 to <3 years, ≥3 year to <7 years, ≥7 years	Yes/ Time since diagnosis of lupus (years) = (date of first dose in JAIM - date of diagnosis of lupus in original study + 1) / 365.25.
Age at diagnosis of SLE f	Yes	<6 years, ≥6 to <10 years, ≥10 to <17 years, ≥17 to <40 years, ≥40 years	Yes/ Age at diagnosis in years will be calculated as the time interval from the imputed date of birth (01 July in the year of birth collected in the eCRF) to the date of diagnosis in original study.
Any flare at baseline, (SELENA-SLEDAI Flare Index definition)	No	None, Mild/Moderate, Severe	No
SLEDAI-2K score	Yes	(<10 or ≥10)	No
Physician's Global Assessment of Disease Activity score	Yes	Mild (<1.5), Moderate (≥1.5 to ≤2.5), Severe (>2.5)	No
Total systemic Lupus International Collaborating Clinics/American College of Rheumatology (SLICC/ACR) Damage Index score	Yes	None	No
Patient's Global Impression of Severity (PGI-S)	Yes	5 categories: no symptoms, very mild, mild, moderate, severe	No
Number of tender joints (from 28-tender joint count)	Yes	None	No
Number of swollen joints (from 28-tender joint count)	Yes	None	No

## Summary Tables Related to Patient Characteristics

Variable	Continuous Summary	Categorical Summary a	Included in Interim 1 Analysis/ Derivation
Cutaneous Lupus Erythematosus Disease Area and Severity Index (CLASI) Total Activity Score	Yes	CLASI (<10, ≥10)	No
CLASI Total Damage Score	Yes	None	No
Complement C3 levels	Yes	Low (<90mg/dL); Normal or higher (≥90mg/dL)	No
Complement C4 level	Yes	Low (<10mg/dL); Normal or higher (≥ 10mg/dL)	No
Complement C3 and C4 levels	No	Low C3 and/or low C4 levels; high C3 and C4 levels	No
Anti-dsDNA level (positive >15 U/mL)	Yes	Yes, No	No
Complement and Anti-dsDNA level	No	Low complement/anti-dsDNA positive (low C3 and/or C4 levels and anti-dsDNA positive); Others	No
Serum immunoglobulin IgA, IgG, and IgM concentrations	Yes	Less than the lower limit of normal [LLN] (Yes, No)	No
Estimated glomerular filtration rate (eGFR)	Yes	eGFR (<60, ≥60 mL/min/1.73m  )	Yes

## Summary Tables Related to Patient Characteristics

Variable	Continuous Summary	Categorical Summary a	Included in Interim 1 Analysis/ Derivation
British Isles Lupus Assessment Group (BILAG) organ system involvement at baseline (yes or no for each organ system domain). Involvement requires a baseline BILAG disease activity score of A or B.	No	Yes, No	No
BILAG A organ system involvement at baseline (yes or no for each organ system domain). Involvement requires a baseline BILAG disease activity score of A.	No	Yes, No	No
SLEDAI-2K organ system involvement at baseline (yes or no for each organ system domain)	No	Yes, No	No
Anti-Sm+ antinuclear antibodies (positive >10 U/mL)	Yes	Yes, No	No
Anti-RNP+ antinuclear antibodies (positive >10 U/mL)	Yes	Yes, No	No
Anti-Sjögren's-syndrome-related antigen A (SSA/Ro-52) antibodies (positive >10 U/mL)	Yes	Yes, No	No
Anti-Sjögren's-syndrome-related antigen A (SSA/Ro-60) antibodies (positive >10 U/mL)	Yes	Yes, No	No
Anti-Sjögren's-syndrome-related antigen B (also called anti-La [Anti-SSB/La+]) antibodies (positive >10 U/mL)	Yes	Yes, No	No
Anti-phospholipid antibody, overall (if any of cardiolipin IgA, IgG, IgM, beta-2-glycoprotein IgG, beta-2-glycoprotein IgM, or lupus anticoagulant are positive, then overall is positive, otherwise negative)	No	Positive, Negative	No
ANA positive (titer $\geq$ 1:80)	No	Yes, No	No

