3.3. Benefit/Risk Assessment

Phase 2 SLE Data

In the baricitinib Phase 2 SLE clinical Study I4V-MC-JAHH (JAHH), significant benefit for baricitinib 4-mg once daily (QD) treatment over placebo was demonstrated for the primary efficacy endpoint of resolution of arthritis and/or rash, the major secondary efficacy endpoint of SRI-4 response, and important supporting measures, such as flare and lupus low disease activity score (LLDAS) after 24 weeks of treatment. Baricitinib 2-mg QD was numerically better than placebo across these measures, although the results were not statistically significant.

The percentage of patients with at least 1 treatment-emergent adverse event (TEAE) during the 24-week treatment period was 64.8% for placebo, 71.4% for baricitinib 2-mg QD, and 73.1% for baricitinib 4-mg QD. The most common TEAEs (occurring in $\geq 5\%$ of patients in either baricitinib dose group over 24 weeks) were viral upper respiratory tract infection, urinary tract infection, upper respiratory tract infection, pharyngitis, and headache. The proportions of patients who reported viral upper respiratory tract infections were higher for baricitinib-treated patients compared to placebo, but the proportions were similar for the baricitinib 2-mg and 4-mg dose groups. It is important to consider that in SLE, patients are at an increased risk for infections due to predisposing conditions related to impaired cellular and humoral immune functions (Danza and Ruiz-Irastorza 2013), as well as concomitant use of immunosuppressive agents, such as corticosteroids. In the Phase 2 study of baricitinib, there were more serious infections reported in the baricitinib 4-mg group versus the baricitinib 2-mg group or placebo. There were no cases of serious herpes zoster or opportunistic infection, and no reports of tuberculosis (TB). There were no malignancies or major adverse cardiovascular events (MACE) reported. One serious adverse event (SAE) of deep vein thrombosis (DVT) was reported in the baricitinib 4-mg group in a patient with pre-existing antiphospholipid antibodies and pain in the affected limb (right calf) prior to study entry, who was taking a concomitant oral corticosteroid and celecoxib during the study.

Risks Identified in the Baricitinib Program

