## 6.8. Patient Characteristics

Patient demographics and baseline characteristics will be summarized using the mITT population, by treatment group. No formal statistical comparisons will be made among treatment groups, unless otherwise stated. A listing of patient demographics will be provided.

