## **6.11. Efficacy Analyses**

### **6.11.1. General Considerations**

[Table JAIM.6.3](#) includes the description, derivation and definition of missingness of the efficacy and health outcomes measures and endpoints. [Table JAIM.6.4](#) includes the description of the

analysis method, population and primary time point(s) of analysis for efficacy and health outcomes measures. Assessments collected at multiple visits will be analyzed at each visit, in addition to the primary time point. Details of each analysis will follow the general principles described under Analysis Methods in Section [6.4](#).

Table JAIM.6.3. Description and Derivation of Efficacy/Health Outcomes Measures and Endpoints

Measure	Description	Variable	Derivation/Comment	Definition of Missing
SRI-4	SRI-4 is a composite index to measure overall improvement in disease activity (SLEDAI-2K) while ensuring there is no worsening in other organ systems (BILAG and PGA)	SLE Responder Index 4	A decrease in SLEDAI-2K $\geq 4$ (from baseline), and No new BILAG A and no more than 1 new BILAB B organ domain (both compared with baseline), and No worsening in PGA (defined as an increase of 0.3 points [10 mm] from baseline).	Missing, if any component (SLEDAI, BILAG, or PGA) remains missing after each instrument-level imputation rule is applied
SLEDAI-2K	The SLEDAI-2K is a global disease activity instrument that focuses on high-impact disease manifestations across 9 organ domains: constitutional, mucocutaneous, musculoskeletal, vascular, cardiorespiratory, central nervous system, immunologic, renal, and hematologic.	SLEDAI-2K Total Score	Calculated by summing the weighted organ manifestations. For the Renal domain, when the urinary casts, hematuria, and pyuria items are “not done” or “not accessed”, they will be coded as “not present”.	If any item scores or all items are missing (not done or not assessed), but the visit occurred, data for that item can be carried forward if obtained within the previous 36 days of visit.
		Individual Organ Domain Improvement defined by SLEDAI-2K	Among patients with SLEDAI-2K score $>0$ within the organ domain at baseline and able to decrease SLEDAI-2K (from baseline) within each organ domain score, separately.	Missing if any SLEDAI-2K item for that organ domain remains missing after instrument-level imputation rules are applied.

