**Summary Tables Related to Patient Characteristics**

Abbreviations: ANA = antinuclear antibodies; APL = antiphospholipid antibody; BMI = body mass index; dsDNA = double stranded DNA; eCRF = electronic case report form; EQ-5D-5L = 5-level EQ-5D version; FACIT = Functional Assessment of Chronic Illness Therapy; IgA/G/M = immunoglobulin A/G/M; MCS = Mental Component Summary; NRS = Numeric Rating Scale; NSAID = Non-steroidal anti-inflammatory drug; PCS = Physical Component Summary; QIDS SR-16 = Quick Inventory of Depressive Symptomatology; SELENA-SLEDAI = Systemic Lupus Erythematosus Disease Activity Index; SF-36 = Short Form 36; SLE = Systemic Lupus Erythematosus; SLEDAI-2K = Systemic Lupus Erythematosus Disease Activity Index 2000; VAS = Visual Analog Scale; WPAI = Work Productivity and Activity Impairment.

- a This column specifies the levels of the categorical variable to be summarized.
- b Age in years will be calculated as length of the time interval from the imputed date of birth (July 1st in the year of birth collected in the electronic case report form [eCRF]) to the informed consent date. Formula below: age (in years) = (date of informed consent date – imputed date of birth)/365.25.
- c Body Mass Index will be calculated as:  $BMI (kg / m^2) = Weight (kg) / (Height (m))^2$ .
- d ATC codes for selecting medications are provided in [Appendix 1](#).
- e Time since diagnosis of lupus (years) = (date of first dose - date of diagnosis of lupus + 1) / 365.25.
- f Age at diagnosis in years will be calculated as the time interval from the imputed date of birth (July 1st in the year of birth collected in the eCRF) to the date of diagnosis.
- g Only applied for Employment Status at baseline is "Yes", except the Activity Impairment Score.

---

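### The overall antiphospholipid row in the SAP's baseline table counts untested and incompletely tested patients as negative, so baseline prevalence can only be understated (low severity)

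*SAP*

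**What the plan says.** The row for overall antiphospholipid antibody in SAP Appendix 2, Table JAIM.APP.1, names its components as follows: "if any of cardiolipin IgA, IgG, IgM, beta-2-glycoprotein IgG, beta-2-glycoprotein IgM", "or lupus anticoagulant are positive, then overall is positive, otherwise negative". That makes six tests and two outcomes. The categorical column lists Positive and Negative only, and footnote a to the table says: "This column specifies the levels of the categorical variable to be summarized".

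The table's population is set in SAP Section 6.8: "Patient demographics and baseline characteristics will be summarized using the mITT population, by treatment group". A patient needs one dose of study treatment to be in that population, not an antibody result.

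The SAP's missing-data definitions are in Table JAIM.6.3. According to Section 6.11.1, that table "includes the description, derivation and definition of missingness of the efficacy and health outcomes measures" and endpoints. Baseline laboratory characteristics are not covered.

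Two nearby rows of Table JAIM.APP.1 are also relevant. The combined complement and anti-dsDNA row has the levels "Low complement/anti-dsDNA positive (low C3 and/or C4 levels and anti-dsDNA positive); Others". The combined complement row has "Low C3 and/or low C4 levels; high C3 and C4 levels", whereas the separate C3 and C4 rows use Low against Normal or higher.

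**The concern.** Not tested and tested negative are different facts, and this row merges them. The rule for Positive needs only one result. The rule for Negative needs none, because it takes in everyone left over. Missing data therefore enter the table as negative findings, and the reader cannot see how many there are.

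Elsewhere the SAP keeps the two apart. In Table JAIM.6.3, SRI-4, BICLA and LLDAS are missing when a component remains missing, and the EQ-5D-5L index is missing when any item is. Where missing is meant to count as absent, as for single items of BILAG, CLASI and the SLICC/ACR Damage Index, the SAP says so. The antiphospholipid row says nothing about missing results.

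At stake is the accuracy of one baseline description, in each treatment group, of a marker with some bearing on VTE, which the protocol lists as an adverse event of special interest.

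**Working it through.** **1. Does the rule do this?** The rule can be applied to each kind of patient:

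| Results available | Any positive? | Reported as | Supported by the data? |
|---|---|---|---|
| All six | Yes | Positive | Yes |
| All six | No | Negative | Yes |
| Some | Yes | Positive | Yes |
| Some | No | Negative | No |
| None | No | Negative | No |

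**2. Does another section override it?** SAP Section 6.8 gives no rule for missing baseline data. Table JAIM.6.3 is limited to efficacy and health outcomes. The baseline definitions in Section 6.3 select nonmissing pre-dose measurements. That may recover an earlier result but does not help a patient who has none. The answer is no.

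**3. Direction.** Every patient in the last two rows goes to Negative and none to Positive. The reported positive share therefore cannot exceed the share that complete testing would show. This needs no assumption about why results are missing.

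**4. Size.** The plan states no figure to reproduce, and it gives neither prevalence nor missingness. The inputs below are assumptions, with missingness taken as unrelated to status.

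*Whole panel missing.* Let p be the true positive share and m the share with no result. Then reported share = p × (1 − m), and understatement = p × m.

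| p | m | Reported | Understatement |
|---|---|---|---|
| 30% | 1% | 29.7% | 0.3 points |
| 30% | 5% | 28.5% | 1.5 points |
| 30% | 10% | 27.0% | 3.0 points |
| 30% | 20% | 24.0% | 6.0 points |

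Over p = 20% to 40% and m = 1% to 20%, the range is 0.20 × 0.01 = 0.2 points to 0.40 × 0.20 = 8.0 points. Scaled to the planned 1,100 patients with p = 30% and m = 5%, 1,100 × 0.05 = 55 patients without a result would be counted as Negative, and 55 × 0.30 = 16.5 of them would truly be positive.

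*Lupus anticoagulant alone missing.* Understatement = share missing that test × share positive on that test only. With 5% and 5% it is 0.25 points (about 3 of 1,100). With 20% and 15% it is 3.0 points (33 of 1,100).

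*Any of the six missing.* If each is missing independently with probability q, the share lacking at least one is 1 − (1 − q)^6: 5.9% at q = 1%, 11.4% at 2% and 26.5% at 5%. These patients are coded Negative unless another test is positive. Independence is an assumption; gaps from a missed draw would cluster.

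**5. Would dropping Unknown patients from the denominator cure it?** No. Partly tested positives would stay in while partly tested patients without a positive would leave. Let a be the share missing lupus anticoagulant and s the share positive on it alone. The percentage becomes (p − a × s) / (1 − a × (1 − (p − s))).

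| p | a | s | SAP rule | Unknown dropped |
|---|---|---|---|---|
| 30% | 5% | 5% | 29.75% | 29.75 / 96.25 = 30.9% |
| 30% | 20% | 15% | 27.0% | 27.0 / 83.0 = 32.5% |
| 40% | 20% | 15% | 37.0% | 37.0 / 85.0 = 43.5% |

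That error is of similar or larger size and points the other way. A percentage confined to patients with all six results returns p under the same assumption.

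**The case against.** The strongest reply is that little depends on this row. It is summarised descriptively by treatment group and is marked No for the first interim analysis. All three antibody groups are scheduled at Visit 1 in the protocol's Schedule of Activities, so gaps would be missed or failed samples and not a product of the design. All of this stands, and it is why the severity is low.

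A reader might infer that VTE cases in untested patients would be misread as arising without a risk factor. The documents do not support that. Suspected events go individually to a blinded committee (protocol Section 9.4.9), and antiphospholipid tests are among those that may be obtained after a confirmed event (protocol Appendix 5). SAP Section 6.14.5 sends special safety topics to the integrated plan, which is not available here. Nothing says that an event would be read from this summary flag.

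A reader might also infer that the protocol explains its Phase 2 deep vein thrombosis by these antibodies. Protocol Section 3.3 says that the event "was reported in the baricitinib 4-mg group in a patient with pre-existing antiphospholipid antibodies", but the same sentence adds earlier pain in the affected limb and concomitant oral corticosteroid and celecoxib. The antibodies are one listed feature among several.

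Finally, other categorical rows, such as eGFR and ANA, list no missing level either. That is true, but they contain no instruction that assigns a missing value to a category. This row does, so the objection does not remove the point.

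The neighbouring rows are weaker cases. Others in the complement and anti-dsDNA row is openly a residual label and calls no one negative. The word high in the combined complement row can only mean not low, since no upper cut-off is given, so it is loose wording and not a missing-data fault.

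**Conclusion.** The point holds as a wrong derivation rule for one baseline row. Patients with no results, or with an incomplete panel and no positive result, are reported as Negative. The reported prevalence can therefore be too low but never too high. The direction follows from the rule alone.

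The size cannot be taken from the documents. The 0.2 to 8.0 points rest wholly on assumed prevalence and missingness, and the true figure could be near zero if Visit 1 sampling is complete. No conclusion about VTE risk in this study is shown to depend on the row. Severity is low; the correction is worth making because it is cheap and the present rule hides how many patients were not fully tested.

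**What to change.** In Table JAIM.APP.1, reword the overall antiphospholipid row:

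- **Positive** if any of the six tests is positive.
- **Negative** only if all six are available and negative.
- **Unknown** otherwise, split into no results and incomplete panel without a positive.

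Show all counts as percentages of the full treatment group. Do not remove Unknown patients from the denominator while keeping partly tested positives. If a percentage among tested patients is wanted, base both numerator and denominator on patients with all six results.

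In the complement and anti-dsDNA row, set to missing only those whose status cannot be settled from the available results. A patient known to be anti-dsDNA negative, or known to have neither complement low, belongs in Others whatever else is missing. As an editorial alignment with the single-test rows, change the second level of the combined C3 and C4 row to normal or higher for both.

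The cost is extra lines of counts and minor reprogramming. SAP Appendix 2 states that changes to this table need no SAP amendment.
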